APPENDIX II – CLINICAL SIGNS AND ARCHITECTURAL CHANGES SEVERITY SCALE*

At baseline, prior to treatments and at the four follow-up visits, the study investigator will complete assessments for severity of the following clinical signs associated with vulvar lichen sclerosus.

Sign	Presence of signs	Severity
Fissures	Yes / No	1, mild 2, moderate 3, severe
Whitening	Yes / No	1, mild 2, moderate 3, severe
Crinkly/fine wrinkling of skin/parchment-like skin	Yes / No	1, mild 2, moderate 3, severe
Extent of disease (figure of eight vs localized to labia, localized to clitoris, localized to perineum or combined)	Yes / No	1, mild 2, moderate 3, severe
Erosions	Yes / No	1, mild 2, moderate 3, severe
Ulcerations	Yes / No	1, mild 2, moderate 3, severe

Hyperkeratosis	Yes / No	1, mild 2, moderate 3, severe
Excoriations	Yes / No	1, mild 2, moderate 3, severe
Lichenification	Yes / No	1, mild 2, moderate 3, severe
Elasticity (or loss of elasticity)	Yes / No	1, mild 2, moderate 3, severe
Sclerosis	Yes / No	1, mild 2, moderate 3, severe
Telangiectasia	Yes / No	1, mild 2, moderate 3, severe

Architectural changes	Presence of changes	Severity
Clitoral hood fusion	Yes / No	1, mild 2, moderate 3, severe
Labial fusion/resorption	Yes / No	1, mild 2, moderate 3, severe

Narrowing of the introitus	Yes / No	1, mild 2, moderate 3, severe
Anterior changes (fusion anteriorly below the clitoris, causing	Yes / No	1, mild 2, moderate 3, severe
urethral occlusion at its extreme)	Yes / No	1, mild 2, moderate 3, severe
Perianal involvement	Yes / No	1, mild 2, moderate 3, severe
Formation of posterior commissure bands/fourchette webs	Yes / No	1, mild 2, moderate 3, severe

APPENDIX III – FEMALE SEXUAL FUNCTION INDEX*
Female Sexual Function Index (FSFI) ®

Subject Identifier _____ Date _____

INSTRUCTIONS: These questions ask about your sexual feelings and responses during the past 4 weeks. Please answer the following questions as honestly and clearly as possible. Your responses will be kept completely confidential. In answering these questions the following definitions apply:

Sexual activity can include caressing, foreplay, masturbation and vaginal intercourse.

Sexual intercourse is defined as penile penetration (entry) of the vagina.

Sexual stimulation includes situations like foreplay with a partner, self-stimulation (masturbation), or sexual fantasy.

CHECK ONLY ONE BOX PER QUESTION.

Sexual desire or interest is a feeling that includes wanting to have a sexual experience, feeling receptive to a partner's sexual initiation, and thinking or fantasizing about having sex.

1. Over the past 4 weeks, how often did you feel sexual desire or interest?

- Almost always or always
- Most times (more than half the time)
- Sometimes (about half the time)
- A few times (less than half the time)
- Almost never or never

2. Over the past 4 weeks, how would you rate your level (degree) of sexual desire or interest?

- Very high
- High
- Moderate
- Low
- Very low or none at all

Sexual arousal is a feeling that includes both physical and mental aspects of sexual excitement. It may include feelings of warmth or tingling in the genitals, lubrication (wetness), or muscle contractions.

3. Over the past 4 weeks, how often did you feel sexually aroused ("turned on") during sexual activity or intercourse?

No sexual activity
 Almost always or always
 Most times (more than half the time)
 Sometimes (about half the time)
 A few times (less than half the time)
 Almost never or never

4. Over the past 4 weeks, how would you rate your level of sexual arousal ("turn on") during sexual activity or intercourse?

No sexual activity
 Very high
 High
 Moderate
 Low
 Very low or none at all

5. Over the past 4 weeks, how confident were you about becoming sexually aroused during sexual activity or intercourse?

No sexual activity
 Very high confidence
 High confidence
 Moderate confidence
 Low confidence
 Very low or no confidence

6. Over the past 4 weeks, how often have you been satisfied with your arousal (excitement) during sexual activity or intercourse?

No sexual activity
 Almost always or always
 Most times (more than half the time)
 Sometimes (about half the time)
 A few times (less than half the time)
 Almost never or never

7. Over the past 4 weeks, how often did you become lubricated ("wet") during sexual activity or intercourse?

No sexual activity
 Almost always or always
 Most times (more than half the time)
 Sometimes (about half the time)
 A few times (less than half the time)
 Almost never or never

8. Over the past 4 weeks, how difficult was it to become lubricated ("wet") during sexual activity or intercourse?

No sexual activity
 Extremely difficult or impossible
 Very difficult
 Difficult
 Slightly difficult
 Not difficult

9. Over the past 4 weeks, how often did you maintain your lubrication ("wetness") until completion of sexual activity or intercourse?

No sexual activity
 Almost always or always
 Most times (more than half the time)
 Sometimes (about half the time)
 A few times (less than half the time)
 Almost never or never

10. Over the past 4 weeks, how difficult was it to maintain your lubrication ("wetness") until completion of sexual activity or intercourse?

No sexual activity
 Extremely difficult or impossible
 Very difficult
 Difficult
 Slightly difficult
 Not difficult

11. Over the past 4 weeks, when you had sexual stimulation or intercourse, how often did you reach orgasm (climax)?

- No sexual activity
- Almost always or always
- Most times (more than half the time)
- Sometimes (about half the time)
- A few times (less than half the time)
- Almost never or never

12. Over the past 4 weeks, when you had sexual stimulation or intercourse, how difficult was it for you to reach orgasm (climax)?

- No sexual activity
- Extremely difficult or impossible
- Very difficult
- Difficult
- Slightly difficult
- Not difficult

13. Over the past 4 weeks, how satisfied were you with your ability to reach orgasm (climax) during sexual activity or intercourse?

- No sexual activity
- Very satisfied
- Moderately satisfied
- About equally satisfied and dissatisfied
- Moderately dissatisfied
- Very dissatisfied

14. Over the past 4 weeks, how satisfied have you been with the amount of emotional closeness during sexual activity between you and your partner?

- No sexual activity
- Very satisfied
- Moderately satisfied
- About equally satisfied and dissatisfied
- Moderately dissatisfied
- Very dissatisfied

15. Over the past 4 weeks, how satisfied have you been with your sexual relationship with your partner?

- Very satisfied
- Moderately satisfied
- About equally satisfied and dissatisfied
- Moderately dissatisfied
- Very dissatisfied

16. Over the past 4 weeks, how satisfied have you been with your overall sexual life?

- Very satisfied
- Moderately satisfied
- About equally satisfied and dissatisfied
- Moderately dissatisfied
- Very dissatisfied

17. Over the past 4 weeks, how often did you experience discomfort or pain during vaginal penetration?

- Did not attempt intercourse
- Almost always or always
- Most times (more than half the time)
- Sometimes (about half the time)
- A few times (less than half the time)
- Almost never or never

18. Over the past 4 weeks, how often did you experience discomfort or pain following vaginal penetration?

- Did not attempt intercourse
- Almost always or always
- Most times (more than half the time)
- Sometimes (about half the time)
- A few times (less than half the time)
- Almost never or never

19. Over the past 4 weeks, how would you rate your level (degree) of discomfort or pain during or following vaginal penetration?

- Did not attempt intercourse
- Very high
- High
- Moderate
- Low
- Very low or none at all

Thank you for completing this questionnaire

Copyright ©2000 All Rights Reserved

Page 5 (of 5)

[figure not shown]
APPENDIX IV – PHOTOGRAPHY GUIDELINES

At each time point (before the treatments and at the follow-up visits), photographs of the treated area should be taken in a standardized manner.

- Photographs should be taken in a private room or area of the clinic under controlled conditions, including the distance from the camera to the subject, height of the camera, background, camera positioning, subject's positioning and lighting in order to achieve high quality before & after sets.
- For consistency purposes, the same person should ideally take all study photographs, especially per subject.
- Small plain labels (with the date, subject ID, subject initials, Investigator name, and identity of the specific area photographed, if necessary) should be placed in the same location within each frame at each photography timepoint. The presence of the label should not impair the photo's desired effect or obscure the treated area.
- The digital files should be labeled in a standardized manner (subject number, subject initials, study visit). For example: 001JS_Tx1, 001JS_FU1, etc.

APPENDIX V – TREATMENT-ASSOCIATED PAIN ASSESSMENT

Immediately after each treatment, the subject will be asked to rate pain/discomfort associated with the treatment, based on the following Numerical Scale Response (NSR). The subject will be given a horizontal line scale and asked to make a mark along the scale. The subject will be asked to rate pain from 0 to 10, with 0 equaling no pain and 10 equaling the worst possible pain. A number is obtained by measuring up to the point the subject has indicated.

APPENDIX VI – SUBJECT POST-TREATMENT DAILY DIARY QUESTIONNAIRE

At the 1st treatment study visit, subjects will be provided with a 1-week daily diary and instructed to rate the discomfort they experienced on the day of treatment and each day following treatment, according to the following scale:

	Score and Rate
	0 - No Discomfort
	1 - Mild Discomfort
	2 - Moderate Discomfort, but tolerable
	3 - Very Painful, barely tolerable

Additionally, subjects will be instructed to report any adverse (side) effects during the first week post-treatment and to describe the event on the questionnaire.

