Lichen sclerosus (LS) is a chronic, inflammatory skin disorder of genital and extragenital skin.¹ It most commonly affects the anogenital region of adult women.² Lichen sclerosus (LS) was described for the first time in 1887. Since then, many synonyms have been in use, notably 'Kraurosis vulvae,' 'vulvar dystrophy,' 'white spot disease,' and 'lichen sclerosus et atrophicus' or 'guttate scleroderma.¹ All of these terms have been abandoned and replaced by 'lichen sclerosus,' which is now used for genital and extragenital lesions.¹ LS is a chronically relapsing disease with a potential for atrophy, destructive scarring, functional impairment, and malignant evolution.^{1,3,4} Therefore, early diagnosis, prompt treatment, and long-term follow-up of affected patients are mandatory.¹

It is estimated that up to 20% of all women will experience significant vulvar symptoms at some point in their lifetime.² Although women's health is a topic of growing concern in today's society, conditions such as vulvar lichen sclerosus (VLS) are often underdiagnosed and undertreated. Most cases are diagnosed in postmenopausal women.⁵ The involved skin becomes thin and white, with frequently present bruises or petechiae and anatomic changes. Symptoms include persistent itching and soreness or burning. At advanced stages of lichen sclerosus, scarring after inflammation may lead to severe damage by fusion of the labia, narrowing of the vaginal opening, burying of the clitoris in women and girls and risk of developing squamous cell carcinoma.

The treatment of VLS aims at controlling the symptoms, stopping further scarring and distortion and reducing the risk of cancer. Previously, the gold standard in treatment was ultra-potent topical steroids (i.e. clobetasol propionate).⁵ Currently, mid to high-potent topical steroids are a first-line therapy. The anti-inflammatory properties of clobetasol and other steroids have been most effective in managing associated symptoms, decreasing inflammation, and preventing progression of the condition and subsequent scarring.⁶ Second-line treatments include calcineurin inhibitors, retinoids, and immunosuppressors. Surgery is used only for the treatment of complications associated with VLS.⁵

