Change from baseline in presence and severity of symptoms (5-point severity scale), clinical signs (3-point severity scale) and architectural changes (3-point severity scale) at the 6-week, 3-month, 6-month and 12-month follow-up visits. (**Appendices I & II**).

Secondary Safety Endpoints

Evaluate the safety of the treatment:

1. Clinical evaluation of treated area at each study visit. Clinical photography will be performed for study documentation (**Appendix IV**).
2. Pain/discomfort level using a 10-point Numerical Scale Response (NSR) after each treatment (**Appendix V**).
3. Number, severity and type of adverse events recorded throughout course of the study.
4. 1 week ± 2 days post first treatment safety phone call (review of 1-week patient diary) – (**Appendix VI**).

Secondary Efficacy Endpoints

1. Sexual function, using the Female Sexual Function Index (**Appendix III**), at baseline and at the 3-month and 6-month follow-ups. *An overall score ≤ 26.55 is classified as Female Sexual Disorder (FSD).*¹⁵
2. Histological signs (degree of hyperkeratosis, epidermal atrophy and dermal inflammation) at baseline and at 6 weeks and 6 months after the final treatment.
3. Subject satisfaction, using a 5-point Likert scale (-2=very dissatisfied; 2=Very satisfied), will be assessed at the 6-week, 3-month, 6-month and 12-month follow-up visits (**Appendix VII**).

SUBJECT POPULATION

Up to 45 female subjects who meet the following inclusion / exclusion criteria may be enrolled.

Subject Withdrawal and Replacement

Subjects enrolled in the study can discontinue their participation at any time for any reason without prejudice or reduction in the quality of their medical care. The investigator or sponsor can terminate a subject's participation in this study to protect the subject's health or if the subject fails to follow directions resulting in noncompliance to study procedures. Subjects who withdraw or are terminated from the study may be replaced to allow up to 45 subjects to complete the study. Subjects who fail to complete the treatment will be replaced and will not be evaluable.

Inclusion Criteria

1. Able to read, understand and sign informed consent for study participation;
2. Female subjects with age 18-80 years;
3. Biopsy demonstrates biopsy-proven lichen sclerosus and/or there are characteristic changes for vulvar lichen sclerosus on physical examination;

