4. Treatment of LS has been recalcitrant to mid to high-potent topical corticosteroid treatment or subject refuses topical corticosteroid treatment. Recalcitrance to therapy is defined as no response to topical corticosteroids of an adequate potency (i.e. clobetasol propionate 0.05% ointment or other steroids) and a sufficient duration (12 weeks of use) or lack of symptomatic control of the disease with a maintenance therapy;
5. Topical corticosteroid treatment, if any, will be continued during the study period;
6. Exogenous hormone treatment, if any, will be continued during the study period (type and dose must stay consistent throughout the study);

7. One or more of the following symptoms: itch; pain unrelated to intercourse; pain, skin tearing or bleeding with intercourse; changes/decrease in sexual function;
8. Characteristic changes for vulvar lichen sclerosus on physical examination;
9. No breaks, tears or lesions, malodorous discharge or strawberry cervix present on gynecological exam.

Exclusion Criteria

1. Presence of clinically atypical appearing nevi in the area to be treated;
2. Unexplained vaginal bleeding;
3. Active infection, specifically: urinary tract infection, vulvar or vaginal infection (candidiasis, genital herpes/HSV, bacterial vaginosis, trichomonas);
4. History of vulvar or any gynecological malignancy, as well as history of pelvic radiation therapy or stem cell transplant;
5. Pelvic organ prolapse > stage 2;
6. Pregnancy or planning pregnancy during the study;
7. Systemic treatment with immuno-modulatory drugs.
8. Use of vaginal dilators during study.

STUDY PROCEDURES

Enrollment and Screening

During the first visit, the investigator will screen the subject for eligibility to participate in the clinical study. The inclusion/exclusion criteria will be reviewed, the subject's medical history, an examination of the subject's treatment areas will be conducted.

The subject will review the informed consent form (ICF) and the study will be explained to the subject including all risks, potential benefits, procedures, visit requirements, and other alternative treatment options. If the subject qualifies and wishes to participate they will complete the ICF with a signature and date. The original will be retained with subject's records and a copy will be provided to the subject.

The following measurements will be performed and recorded at the specified times throughout the study (as specified in Error! Reference source not found.).

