Table 2. Study Measurements

Assessment	When to conduct	Method
Complete the Inform Consent form and Eligibility Screening and Medical History	During the screening visit / prior to the 1 st treatment	Physician or staff will complete the form with the study subject
PAP smear if not up-to-date (within 3 years according to ACOG guidelines)		Patient should provide lab results of up-to-date normal cell cytology
Urine pregnancy test for women capable of becoming pregnant		Patient should have a negative pregnancy test
Gynecological exam		Physician will examine the vulvar and vaginal area for any signs of active infection or atypical nevi
Vulvar biopsy of treatment area (optional)	Prior to the 1 st treatment and at the 6-week and 6-month follow-ups	Biopsies will be obtained from up to 10 subjects to conduct histological assessment. Lab reports will be provided to show changes in markers compared to baseline.
Subject assessment of symptoms	
 • Baseline or pre-Tx. 1 • At the 6-week, 3-month, 6-month and 12-month follow-up visits 	Subjects will complete the Symptom Severity Questionnaire, according to the pre-defined scales (Appendix I)
Physician assessment	
 • Baseline or pre-Tx. 1 • Prior to treatments • At the 6-week, 3-month, 6-month and 12-month follow-up visits 	Physician will assess clinical signs associated with VLS, according to the pre-defined scales (Appendix II)
Subject assessment of sexual function	
 • Baseline or pre-Tx. 1 • At the 3-month and 6-month follow-up visits 	Subjects will complete the Female Sexual Function Index (FSFI) – Appendix III
Clinical evaluation and photographs of treated area	
 • Baseline or pre-Tx. 1 • Prior to treatments • At the 6-week, 3-month, 6-month and 12-month follow-up visits 	Physician will evaluate the treatment area. Physician or staff will take photographs of the treatment area (Appendix IV)
Treatment pain assessment	Immediately after each treatment	NSR Scale (Appendix V)
Subject 1-week daily diary - reviewed at the 1wk FU after the first treatment	The daily diary will be provided at the 1 st treatment visit and reviewed by phone during the 1-week safety evaluation	Subjects will be requested to complete a daily diary with data regarding their comfort, AE, and activity (7 days of follow-up post 1st treatment) – Appendix VI

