Following the first treatment:

1. Subjects will receive a daily diary, which they will be requested to complete, regarding their comfort and any adverse events for the 7-day period following treatment.

Following each treatment session

1. If the subject experiences itch or discomfort after treatment, ice packs may be applied to the treatment area.
2. Temporary erythema (redness) and edema (swelling), as well as heat and tightening sensations, may occur up to a few hours after the treatment. If the subject feels significant discomfort longer than a few hours, an over-the-counter pain medication such as Tylenol® (Acetaminophen) may be used. Nonsteroidal anti-inflammatory drugs (NSAID), such as aspirin, Ibuprofen (Advil, Motrin), naproxen (Aleve, Anaprox, Naprelan, Naprosyn), etc. should be avoided unless the patient does not experience symptomatic relief with or is contraindicated to acetaminophen.
3. On the evening after the treatment, subjects should wash the treated areas gently with lukewarm water and avoid very hot or cold water in these areas. Generally, subjects may use their regular cleanser after treatment, as long as these are not mechanical scrubs or exfoliants.
4. Subject should refrain from sexual activities for a period of 7 days.
5. Any pain, fever or unusual discharge should be immediately reported.

 Candela Corporation Confidential	Clinical Study of the CO₂RE Laser Device for Treatment of Vulvar Lichen Sclerosus				
	Protocol #	DHF25211	Rev. Date	February 19, 2019	Page 16 of 39

Follow-up Visits

1. All subjects will be requested to return to the clinic at the following time-points during the study to assess the clinical safety and performance of the device:
 - 6 weeks post last treatment – 6wk FU ± 2 weeks.
 - 3 months post last treatment – 3m FU ± 2 weeks.
 - 6 months post last treatment – 6m FU ± 2 weeks.
 - 12 months post last treatment – 12m FU ± 2 weeks.
2. At the follow-up visits, the following assessments will be performed, and data recorded:
 - Review changes in medication, medical history and AE, if applicable, from last visit.
 - Photographs of treated area.
 - Optional biopsy of treated area (6-week and 6-month follow-up only).
 - Subject assessment of symptom severity.
 - Investigator assessment of clinical signs.
 - Subject Satisfaction.

DATA ANALYSIS

Recording

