APPENDIX I – SUBJECT SYMPTOMS SEVERITY SCALE*

At baseline and at the four follow-up visits, the study subject will complete assessments for severity of the following symptoms associated with their vulvar lichen sclerosus.

Subject Symptoms

Symptom	Presence of symptoms	Severity
Itch	Yes / No	1, absent/never 2, sometimes/occasionally 3, often 4, most of the time 5, all the time
Pain unrelated to intercourse (burning, soreness, discomfort, etc.)	Yes / No	1, absent/never 2, sometimes/occasionally 3, often 4, most of the time 5, all the time
Superficial (introital) dyspareunia (pain occurring at the moment of penetration)	Yes / No	1, absent/never 2, sometimes/occasionally 3, often 4, most of the time 5, all the time

Skin tearing or external bleeding with intercourse	Yes / No	1, absent/never 2, sometimes/occasionally 3, often 4, most of the time 5, all the time
Quality of life	Yes / No	1, no impact 2, barely affected 3, slightly affected 4, moderately affected 5, strongly affected
Decrease in sexual function – desire to have sexual intercourse is decreased due to physical appearance or self-esteem	Yes / No	1, no impact 2, barely affected 3, slightly affected 4, moderately affected 5, strongly affected

*Based on: Sheinis M, Selk A. Development of the Adult Vulvar Lichen Sclerosus Severity Scale-A Delphi Consensus Exercise for Item Generation. J Low Genit Tract Dis. 2018 Jan;22(1):66-73. doi: 10.1097/LGT.0000000000000361.

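### The one-week diary rates all discomfort with no pre-treatment rating on the same 0–3 scale, so for women who enter with itch or pain it cannot separate disease from laser

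*Protocol*

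**What the plan says.** **The diary.** Under Appendix VI, women are "instructed to rate the discomfort they experienced on the day of treatment and each day following treatment". The scale runs from 0 (none) to 3 (barely tolerable). Table 2 fixes the timing: "The daily diary will be provided at the 1 st treatment visit and reviewed by phone during the 1-week safety evaluation". The post-treatment instructions describe its content as "regarding their comfort and any adverse events for the 7-day period following treatment".

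**Its role.** Item 4 of the Secondary Safety Endpoints is the "post first treatment safety phone call (review of 1-week patient diary"). The synopsis lists the same call among the safety endpoints.

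**Who is enrolled.** Inclusion criterion 7 requires "One or more of the following symptoms: itch; pain unrelated to intercourse", or one of several symptoms related to intercourse or sexual function. The Background says of the disease in general: "Symptoms include persistent itching and soreness or burning".

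**Other measures of discomfort.** The numerical pain scale in Appendix V is taken immediately after each treatment and asks the woman to "rate pain/discomfort associated with the treatment". Before treatment, women complete the Appendix I symptom scale and the FSFI. Appendix I includes the item "Pain unrelated to intercourse (burning, soreness, discomfort, etc.)", scored 1 to 5 by how often it occurs.

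**The concern.** The diary is the only scaled rating of discomfort in the days after the laser. It asks how much discomfort the woman has, whatever the cause, and starts on the day of treatment. Some of these women will already have itch, burning or soreness, since those are among the symptoms that qualify them for entry. There is no untreated group and no earlier rating on the same scale, so nothing shows what the score would have been without the laser.

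At stake is whether a listed safety measure can be interpreted. If diary scores are summarised, a reader will want to know how much discomfort the procedure added in the following week, and the data as collected cannot say. No analysis plan can repair this later, because it would need a rating that was never taken.

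**Working it through.** The documents give no expected diary scores and no baseline discomfort level, so there is no plan figure to reproduce. The check sets the relevant sections side by side.

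1. **Attribution.** Appendix V ties its rating to the treatment in words ("rate pain/discomfort associated with the treatment"). Appendix VI has no such words. Its title places the diary after treatment, but that states timing and not cause.

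2. **A rating before the laser.** The diary is handed out at the first treatment visit. The screening and baseline list names two questionnaires, the symptom scale and the FSFI. Table 2 adds no 0–3 discomfort rating before treatment 1.

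3. **Substitutes among the baseline measures.**
   - Appendix I covers itch and non-intercourse pain, but grades frequency from absent to constant. A constant mild soreness and a constant severe one get the same score, so it cannot be subtracted from an intensity rating. It can identify women who report neither itch nor pain at baseline.
   - FSFI items 17–19 ask about discomfort or pain, and item 19 grades its degree, but all three concern vaginal penetration. Women are asked to abstain from sex for 7 days after treatment, which is the diary week, so these items do not describe what the diary measures.

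4. **Substitutes among the post-treatment measures.** The Appendix V scale is taken once, straight after each session, and the Immediately Post Treatment section describes it as pain felt while being treated. It says nothing about the following days. Adverse events written in the diary can be judged for relationship to the device under the adverse-event definitions. The 0–3 score has no such step.

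5. **What follows for one woman.** As a simplification, write diary score = usual discomfort + discomfort added by the laser.
   - Woman A: usual 2, added 0. Diary score 2 + 0 = 2.
   - Woman B: usual 0, added 2. Diary score 0 + 2 = 2.

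   The diaries are identical. With a pre-treatment rating on the same scale, the differences are 2 − 2 = 0 and 2 − 0 = 2, and the two women are told apart. Without it there are two unknowns and one observation, and the single-arm design offers no group from which to estimate either.

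**The case against.** The case on the other side is substantial, and much of it stands.

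- **The diary supports a safety call.** Its listed use is review by a nurse at one week. For catching problems, recording all discomfort whatever its cause is a sensible and cautious choice. This stands, and it is a reason to keep the raw rating.
- **Treatment discomfort has its own attributed measure.** The Appendix V scale is taken after every treatment and serves the objective on discomfort following each treatment. This stands for the session itself, but not for the days after.
- **Not every woman is affected.** Criterion 7 can be met by intercourse-related symptoms or reduced sexual function alone, and intercourse-triggered pain should be largely absent during the week of abstinence. The Background sentence describes the disease, not the daily level of the women enrolled. This stands and narrows the point to women with itch or pain unrelated to intercourse.
- **Some information is available.** Appendix I can separate women without baseline symptoms, whose ratings are largely free of the problem, and a falling daily course hints at a transient component. This stands in part: for symptomatic women the level to which the score should fall is still unknown.

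A reader might go further and infer that disease discomfort will be reported as caused by the laser, or that symptomatic women will be shown as never recovering. The protocol does not support either reading. It fixes no summary or attribution rule for diary scores, and time to recovery is neither an objective nor an endpoint. Nor can the number of affected diaries be estimated, since the protocol gives no baseline discomfort figure.

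**Conclusion.** The point holds in a limited form. For women who enter with itch or pain unrelated to intercourse, the diary score in the week after treatment 1 mixes disease discomfort with any discomfort added by the laser, and the design gives no means of separating them.

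The conclusion rests on the diary wording, its first issue at treatment 1, the absence of a 0–3 rating beforehand, and the single arm. All of these are in the protocol. It also assumes that some enrolled women have day-to-day discomfort before treatment. The entry criteria make that likely, but no figure is given, so the size of the mixing is unknown.

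Severity is minor. This is a secondary safety measure covering one week after the first of up to five treatments. The primary endpoint, the Appendix V pain scores and the adverse-event assessment are untouched. It is worth raising because the missing rating cannot be recovered later and costs almost nothing to collect.

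**What to change.** Add one row to the Appendix VI form: the same 0–3 item, asking for usual discomfort in the treated area over the past 7 days, completed before any biopsy, anesthetic or laser. Screening may take place on a separate day, so a woman biopsied at that visit needs the row then, ahead of the handover of the diary at treatment 1.

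For each diary day, report the raw ratings and the number of women above their own pre-treatment rating. Show the biopsied women (up to 10) separately, because soreness from the biopsy can also lift the score above the pre-treatment value. State how many women rated 3 beforehand, since they cannot score higher.

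The cost is one question per woman and one derived variable. The limitation is that a single recalled rating for the past week is only an approximate baseline for ratings made day by day. It makes the score interpretable but does not prove cause.
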